1 INTRODUCTION

1.1 Hemophilia A

Hemophilia A is an inherited sex-linked disorder of blood coagulation in which affected males do not produce functional coagulation factor VIII (FVIII) in sufficient quantities to achieve satisfactory hemostasis. The incidence of congenital hemophilia A is approximately 1 in 10,000 births. Disease severity is classified according to the level of FVIII activity (% of normal) as mild (>5% to <40%), moderate (1% to 5%), or severe (<1%).

The deficiency in FVIII predisposes patients with hemophilia A to recurrent bleeding episodes (BEs) in joints, muscles, or internal organs, either spontaneously or as a result of accidental or surgical trauma. Without adequate treatment, these repeated hemarthroses and hematomas lead to long-term sequelae with severe disability. Less frequent but more severe bleeding sites are the central nervous system, the urinary or gastrointestinal tract, the eyes, and the retroperitoneum.

Patients with hemophilia A are at high risk of developing major and life-threatening BEs after surgical procedures, even after minor interventions such as tooth extraction. Replacement therapy with exogenous FVIII, either plasma-derived or recombinant, successfully adjusts hemostasis in these patients in a temporary manner.

1.2 Wilate

Wilate is a plasma-derived, stable, highly purified, double virus inactivated concentrate of freeze-dried active von Willebrand factor (VWF) and factor VIII (FVIII) prepared from cryoprecipitate and intended for the treatment of patients with von Willebrand disease (VWD) and/or hemophilia A. By introducing new biotechnological methods and optimized chromatographic media into the Wilate manufacturing process, it has been possible to manufacture a preparation containing the FVIII/VWF complex in its native form and almost devoid of lower molecular weight proteins.

Overall, 14 prospective clinical studies with *Wilate* have been completed, 8 in patients with VWD and 6 in patients with hemophilia A. The 6 clinical studies with *Wilate* in patients with hemophilia A were open, non-controlled studies investigating the efficacy and safety of the product in the prevention and treatment of BEs as well as in surgical prophylaxis in a total of 109 individual patients with severe hemophilia A. Of these, 81 were previously treated patients (PTPs) and 28 were previously untreated patients (PUPs).

Five of the 6 studies investigated the efficacy of *Wilate* both in the prevention and treatment of BEs and in surgical prophylaxis, and 1 study assessed the efficacy of *Wilate* in surgical prophylaxis only.

Wilate received its first market authorization in Germany in February 2005 and is currently licensed in 65 countries worldwide. In Europe, Wilate is approved for the treatment of both VWD and hemophilia A. In the USA, it is approved for the treatment of VWD only.

This study (WIL-30) in children aged 1 to <12 years is performed to obtain approval of *Wilate* for the treatment of hemophilia A in the USA and is carried out alongside a similar study (WIL-27) in patients with severe hemophilia $A \ge 12$ years of age.

A summary of findings from nonclinical and clinical studies with *Wilate* is provided in the product's Investigator's Brochure.

1.3 Rationale for Conducting the Study

The purpose of this study is to obtain additional data on the PK profile, safety, and efficacy of *Wilate* in previously treated children with hemophilia A, thus supplementing the existing database to obtain approval of *Wilate* for the indication hemophilia A in the USA.

1.4 Dose Rationale

1.4.1 Dose for PK Assessment

The dose used for PK assessment, i.e., 50 ± 5 IU/kg, is in line with the current recommendations of the *Guideline on the clinical investigation of recombinant and human plasma-derived factor VIII products* (EMA/CHPM/BPWP/144533/2009), which recommends a dose of 25–50 IU/kg. It is expected that this dose will result in measurable FVIII:C plasma concentrations after 48 hours in most, if not all, patients.

The \pm 5 IU/kg range (rather than a fixed dose) was included to allow the entire contents of reconstituted vials to be injected rather than taking out an exact volume, which is difficult technically and might result in dosing errors.

1.4.2 Doses for Prophylaxis

The doses for prophylaxis (20–40 IU/kg *Wilate*/kg BW given at intervals of 2 to 3 days), the treatment of BEs and perioperative prophylaxis (see **Section 5.4**), are as indicated in the European Summary of Product Characteristics.

Alternative prophylactic regimens at the discretion of the Investigator are also acceptable.

1.5 Benefit-Risk Statement

The following adverse reactions are known to occur with other VWF/FVIII preparations and may also occur with the use of *Wilate*:

- Hypersensitivity or allergic reactions (which may include angioedema, burning, and stinging at the infusion site, chills, flushing, generalized urticaria, headache, hives, hypotension, lethargy, nausea, restlessness, tachycardia, tightness of the chest, tingling, vomiting, wheezing) have been observed upon use of *Wilate* and may, in some cases, progress to severe anaphylaxis (including shock) with or without fever. In rare occasions, fever has been observed.
- The **formation of neutralizing antibodies (inhibitors) to FVIII** is a known complication in the management of hemophilia A. These inhibitors are usually IgG immunoglobulins directed against the FVIII procoagulant activity, which are quantified in Bethesda Units (BU) per mL of plasma. As preventive measure, hemophilia A patients should not be switched thoughtlessly from one FVIII concentrate to another. Patients should be carefully monitored for the development of inhibitors by appropriate clinical observations and laboratory tests.
- As for all medicinal products prepared from human blood or plasma, infectious diseases due to transmission of infective agents cannot be totally excluded. This applies also to pathogens of hitherto unknown origin. The manufacturing process of *Wilate*, which includes 2 viral inactivation steps with different chemical/physical action principles represents a high standard for plasma-derived concentrates in terms of pathogen safety. The measures taken are considered effective for enveloped viruses such as human immunodeficiency virus (HIV), hepatitis B virus (HBV) and hepatitis C virus (HCV), and for the non-enveloped hepatitis A virus. The measures taken may be of limited value against non-enveloped viruses such as parvovirus B19.

In view of its state-of-the-art manufacturing process and available clinical and postmarketing evidence, the benefit-risk evaluation of *Wilate* is positive.

2 STUDY OBJECTIVES

2.1 Primary Objective

The primary objective of this study is to determine the **FVIII:C pharmacokinetics (PK) for** *Wilate* in previously treated patients (PTP) with severe hemophilia A aged 1 to <12 years.

2.2 Secondary Objectives

The secondary objectives of this study are to:

- Determine the efficacy of Wilate in prophylactic treatment
- Determine the efficacy of *Wilate* in the treatment of breakthrough bleeding episodes (BEs)
- Calculate the **FVIII:C incremental IVR** of *Wilate* over time (at baseline, and at 3 and 6 months of treatment)
- Assess the association between AB0 blood type and the FVIII:C half-life of Wilate
- Assess the association between the VWF:Ag concentration and the FVIII:C half-life of *Wilate*
- Assess the safety and tolerability of Wilate
- Assess the **immunogenicity** of *Wilate*

2.3 Additional Objective

An additional objective of this study is the descriptive **efficacy of** *Wilate* **in surgical prophylaxis**.

3 INVESTIGATIONAL PLAN

3.1 Study Endpoints

3.1.1 Primary Endpoint

The primary endpoint of this study is the PK profile of *Wilate*.

The PK profile is based on the following baseline PK parameters for FVIII:C using both the chromogenic (CHR) and one-stage (OS) assays and actual IMP potencies:

- Area under the curve (AUC) and AUC normalized for the administered dose (AUC_{norm})
- In vivo half-life $(T_{1/2})$
- Maximum plasma concentration (C_{max})
- Time to reach maximum plasma concentration (T_{max})
- Mean residence time (MRT)
- Volume of distribution (Vd)
- Clearance (CL)
- Incremental in vivo recovery (IVR)

3.1.2 Secondary Endpoints

The secondary endpoints of this study are the:

- 1. Total annualized bleeding rate (TABR)
 - TABR will be calculated as the total number of BEs in the time period between first dose of IMP and the Study Completion Visit, divided by the duration (in years) between first dose of IMP and the Study Completion Visit. Surgery periods, and BEs occurring within these periods, will be excluded from the calculation of TABR.
- 2. Spontaneous annualized bleeding rate (SABR), calculated in analogy with TABR
- 3. Efficacy of *Wilate* in the treatment of breakthrough BEs based on the proportion of BEs successfully treated with *Wilate*
- 4. Wilate consumption data (FVIII IU/kg per week per patient) for prophylaxis
- 5. Incremental IVR of *Wilate* over time (at baseline, and at 3 and 6 months of treatment)
- 6. Association between AB0 blood type and the FVIII:C half-life of Wilate
- 7. Association between VWF:Ag concentration and the FVIII:C half-life of Wilate
- 8. Safety and tolerability of *Wilate* by monitoring adverse events (AEs) throughout the study
- 9. Immunogenicity of *Wilate* by testing for FVIII inhibitors
- 10. Virus safety in terms of parvovirus B19

3.1.3 Exploratory Endpoint

An exploratory endpoint of this study is the descriptive efficacy of *Wilate* in surgical prophylaxis.

3.2 Overall Study Design and Plan

This is a prospective, non-controlled, international, multi-center phase 3 study investigating the FVIII:C pharmacokinetics, efficacy, safety, and immunogenicity of *Wilate* in previously treated children with severe hemophilia A aged 1 to <12 years.

Overall, 10 PTPs (5 patients aged 1 to <6 years of age and 5 patients aged 6 to <12 years) will be enrolled into this study by approximately 5 study sites in Europe. The aim is to obtain data on 8 patients (4 patients per age group) who are evaluable for the primary endpoint, i.e., the PK profile of *Wilate*. Enrolled patients will be replaced only if they do not complete the PK assessment.

At baseline, all patients will undergo a 2-day PK Assessment Phase of 1 dose of 50 IU \pm 5 IU Wilate/kg BW. The study is scheduled to start in the 4th quarter of 2017 and to be completed in the 3rd quarter of 2018. The planned duration for an individual patient is at least 6 months (\pm 2 weeks) and at least 50 EDs, plus a Follow-up Contact 30 (\pm 3) days after the Completion Visit.

The primary objective of this study is to determine the FVIII:C pharmacokinetics for *Wilate*. Secondary objectives of this study include the total and spontaneous annualized bleeding rates, the efficacy of *Wilate* in the treatment of breakthrough BEs as well as the product's safety and tolerability. An additional objective is the descriptive efficacy of *Wilate* in surgical prophylaxis.

3.3 Discussion of Study Design

This prospective, non-controlled, international, multi-center phase 3 study was designed keeping in mind the FDA Draft 'Guidance for Industry on the General Clinical Pharmacology Considerations for Pediatric Studies for Drugs and Biological Products.' For the choice of the sample size we used the feedback provided by FDA with regard to the number of patients needed in a different paediatric age group in the WIL-27 study (IND 17181, FDA advice / information request dated 13-Dec-2016).

Because clearance of FVIII differs between adolescents and children, this study in children aged 1 to <12 years is performed to complement PK data on *Wilate* in adolescents and adults.

During the study, safety and efficacy data will also be collected.

4 STUDY POPULATION

4.1 Population Base

4.1.1 Number of Patients

Overall, 10 PTPs (5 patients aged 1 to <6 years of age and 5 patients aged 6 to <12 years) will be enrolled into this study.

The aim is to obtain evaluable data on 8 patients who complete both the 2-day PK Phase and the 6-month Prophylactic Treatment Phase. Of the 8 evaluable patients, 4 patients must be 1 to <6 years of age, and another 4 patients must be 6 to <12 years of age. Enrolled patients will be replaced only if they do not complete the PK assessment.

4.1.2 Inclusion Criteria

Patients who meet all of the following criteria are eligible for the study:

- 1. Severe hemophilia A (<1% FVIII:C) according to medical history
- 2. Male patients aged 1 to <12 years
- 3. Previous treatment with a FVIII concentrate for at least 50 exposure days (EDs)
- 4. Immunocompetence (CD4+ count >200/μL)
- 5. Voluntarily given, fully informed written and signed consent obtained by the patient's parent(s) or legal guardian and, depending on the children's developmental stage and intellectual capacity, informed assent by the patients before any study-related procedures are performed

The interval between the Screening Visit and the PK Visit **should not exceed 30 days**. If the 30-day interval is exceeded, determination of the CD4+ count is to be repeated and must be $>200/\mu$ L for patients to be enrolled (i.e., inclusion criterion no. 4).

4.1.3 Exclusion Criteria

Patients who meet any of the following criteria are *not* eligible for the study:

- 1. Any coagulation disorders other than hemophilia A
- 2. History of FVIII inhibitor activity (≥0.6 BU) or detectable FVIII inhibitory antibodies (≥0.6 BU using the Nijmegen modification of the Bethesda assay) at screening, as determined by the central laboratory
- 3. Severe liver or kidney diseases (alanine aminotransferase [ALAT] and aspartate transaminase [ASAT] levels >5 times of upper limit of normal, creatinine >120 µmol/L)
- 4. Patients receiving or scheduled to receive immunomodulating drugs (other than antiretroviral chemotherapy), such as alpha-interferon, prednisone (equivalent to >10 mg/day), or similar drugs

- 5. Treatment with any investigational medicinal product in another interventional clinical study currently or within 4 weeks before enrollment
- 6. Hemoglobin level < 9 g/dL at the Screening Visit

4.2 Prior and Concomitant Therapy

Patients receiving or scheduled to receive immunomodulating drugs (other than anti-retroviral chemotherapy), such as alpha-interferon, prednisone (equivalent to >10 mg/day), or similar drugs may not be enrolled.

Concomitant therapies not interfering with the objectives of the study are permitted. Details of any concomitant medications must be recorded in the electronic Case Report Form (eCRF).

4.3 Withdrawal and Replacement of Patients

4.3.1 Premature Patient Withdrawal

Patients have the right to withdraw from the study at any time for any reason, without the need to justify their decision. The Investigator also has the right to withdraw patients in case of AEs, poor compliance, or other reasons.

For any withdrawals after study entry, the Investigator will obtain all the required details and document the reason(s) for discontinuation. If the reason for withdrawal of a patient is an AE, the main specific event or laboratory test will be recorded, and the Investigator will make thorough efforts to clearly document the outcome.

4.3.2 Patient Replacement Policy

Enrolled patients will be replaced only if they do not complete the PK assessment.

4.3.3 Assignment of Patients to Treatment

The Investigator will enter a unique identifier for each patient in both the eCRF and the confidential patient identification list and inform the monitor of any new patient enrolled.

Patients who enroll in the study will not be permitted to re-enroll.

4.4 Relevant Protocol Deviations

In case of any major protocol deviation, the Investigator and Octapharma will decide on the further participation of the patient in this study after having discussed all relevant aspects.

5 INVESTIGATIONAL MEDICINAL PRODUCT

5.1 Characterization of Wilate

Wilate, produced from the plasma of human donors, is presented as a powder and solvent for intravenous injection containing nominally 500 IU/1000 IU human von Willebrand factor (VWF) and human FVIII per vial. The ratio between von Willebrand factor ristocetin cofactor activity (VWF:RCo) and FVIII:C is 1:1.

The product contains approximately 100 IU/mL human coagulation factor VIII when reconstituted with 5 mL/10 mL water for injections with 0.1% Polysorbate 80. The FVIII potency (IU) is determined using the European Pharmacopoeia chromogenic assay. The injection or infusion rate should be 2–3 mL per minute.

5.2 Packaging and Labelling

Final labelling will comply with the national requirements of each country where the study is conducted.

5.3 Conditions for Storage and Use

The powder and solvent vials must be stored in a refrigerator (2–8°C). The vials must be kept in the outer carton to protect from light and must not be frozen.

The product can be stored at room temperature (max. 25°C) for 2 months. In this case, the shelf-life expires 2 months after the product has been taken out of the refrigerator for the first time.

The Investigator and any authorized personnel at the site will ensure that the IMP is stored in appropriate conditions with restricted access and in compliance with national regulations.

5.4 Dose and Dosing Schedule

5.4.1 PK Assessment Phase

In the 2-day PK Assessment Phase performed before the start of the Prophylactic Treatment Phase, *Wilate* will be administered to all patients as a single dose of 50 ± 5 IU kg BW.

5.4.2 Prophylactic Treatment Phase

In the Prophylactic Treatment Phase, *Wilate* should be administered every 2 to 3 days at a dose of 20–40 IU/kg BW for 6 months (+2 weeks) and at least 50 EDs.

Alternative prophylactic regimens at the discretion of the Investigator are also acceptable.

In case of unacceptably frequent spontaneous breakthrough BEs (i.e., more than 2 spontaneous BEs or 1 major or life-threatening spontaneous BE within a 30-day period), the dose of *Wilate* should be increased by approximately 5 IU/kg (depending on the entire content of the additional vial(s) that need(s) to be reconstituted).

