7.3.7 Other Relevant Safety Information

(a) Post-study related safety reports

After the Study Completion Visit, any thromboembolic events will continue to be monitored proactively by performing a Follow-up Contact 30 days after the Study Completion Visit (see **Sections 6.1.7** and **7.3.4**). They should be documented on AE page in eCRF.

In addition, any SAE which occurs up to 4 weeks after the last IMP administration should be reported by the Investigator to the Sponsor in case the Investigator becomes aware of it. Proactive monitoring for post-study SAEs is not required.

If any such post-study event is identified, the Investigator will complete an SAE form and transmit it to the Clinical Trial Manager (see **Section 7.3.4**).

Deaths occurring within 4 weeks after the last IMP administration should also be reported, regardless of whether or not they are considered treatment-related.

Overdose, interaction, medication error

The following safety relevant information should be reported as AE or, if the reaction fulfils one of the criteria for seriousness, as SAE.

(b) Drug overdose

An overdose is a deliberate or inadvertent administration of a treatment at a dose higher than specified in the protocol and higher than the known therapeutic dose that is of clinical relevance. The reaction must be clearly identified as an overdose.

(c) Drug interaction

A drug interaction is a situation in which a substance or medicinal product affects the activity of an IMP, i.e., increases or decreases its effects, or produces an effect that none of the products would exhibit on its own. The reaction must be clearly identified as a drug interaction.

(d) Medication error

A medication error involves the inadvertent administration or unintended use of a medicinal product which may be caused by the naming, presentation of pharmaceutical form/packaging, or instructions for use/labelling. The reaction must be clearly identified as a medication error.

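### A prophylaxis dose step of about 5 IU/kg conflicts with giving an entire additional vial: for children dosed in whole vials, that vial adds about 11 to 40 IU/kg

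*Protocol*

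**What the plan says.** Protocol section 5.4.2 states that Wilate "should be administered every 2 to 3 days at a dose of 20–40 IU/kg BW for 6 months", and adds: "Alternative prophylactic regimens at the discretion of the Investigator are also acceptable". Escalation is triggered by "more than 2 spontaneous BEs or 1 major or life-threatening spontaneous BE within a 30-day period". The dose then "should be increased by approximately 5 IU/kg (depending on the entire content of the additional vial(s) that need(s) to be reconstituted". The Study Outline repeats the rule.

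Section 5.1 describes the product as "containing nominally 500 IU/1000 IU human von Willebrand factor (VWF) and human FVIII per vial" and gives the strength: "The product contains approximately 100 IU/mL human coagulation factor VIII when reconstituted with 5 mL/10 mL water for injections". Section 4.1.2 restricts entry to "Male patients aged 1 to <12 years". Section 1.4.1, on the PK dose, explains that a dose range was chosen so that whole vials can be injected, because measuring out an exact volume is awkward and may cause errors.

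SAP version 1.2 computes one TABR and one SABR per child over the prophylactic phase, less surgery phases (section 8.1). It presents prophylaxis efficacy overall and by age group (section 4.6) and lists every IMP treatment (section 5.3). It does not identify children whose dose was raised. Section 4.6 defines a significant dose deviation for the treatment of bleeds, but the SAP has none for prophylaxis.

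**The concern.** The sentence gives a per-kilogram step and, in the same breath, a condition on vial content. With the two vial sizes available, these point to different doses in a child. One site may work to the 5 IU/kg figure and draw up part of a vial. Another may work to the vial condition and give a step several times larger. Both could say they followed the protocol.

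What is at stake is a dosing instruction for young children, used when bleeding is frequent or serious, whose stated size may differ from what is given. On the analysis side, the affected children are selected for bleeding, so they contribute to TABR and SABR. Their consumption in IU/kg per week depends on which reading the site took.

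**Working it through.** **Inputs.** Vials of 500 and 1000 IU at about 100 IU/mL (5.1); stated step of about 5 IU/kg, range 20–40 IU/kg, every 2 to 3 days (5.4.2); 5 children per age group (4.1.1). Body weight is an assumption: 12.5 to 45 kg.

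**Step from one additional vial.** Step (IU/kg) = 500 / body weight (kg). Replacing a 500 IU vial with a 1000 IU vial gives the same 500 IU increment.

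**Can the stated figure be reproduced?** 500 / 5 = 100 kg. Reading the figure loosely, a step of 7.5 IU/kg or less needs 500 / 7.5 = 67 kg or more, and 10 IU/kg or less needs 500 / 10 = 50 kg or more.

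| Weight (kg) | 500 / weight (IU/kg) | Multiple of 5 IU/kg | Whole-vial dose within 20–40 IU/kg | After one more 500 IU |
|---|---|---|---|---|
| 12.5 | 40.0 | 8.0 | 40.0 | 80.0 |
| 15 | 33.3 | 6.7 | 33.3 | 66.7 |
| 20 | 25.0 | 5.0 | 25.0 | 50.0 |
| 25 | 20.0 | 4.0 | 20.0 or 40.0 | 40.0 or 60.0 |
| 30 | 16.7 | 3.3 | 33.3 | 50.0 |
| 40 | 12.5 | 2.5 | 25.0 or 37.5 | 37.5 or 50.0 |
| 45 | 11.1 | 2.2 | 22.2 or 33.3 | 33.3 or 44.4 |

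The lower limit of 12.5 kg is where one whole vial equals 40 IU/kg (500 / 40). Below it, no whole-vial dose lies within 20–40 IU/kg. At 60 kg the step is still 500 / 60 = 8.3 IU/kg.

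**The part-vial reading.** 5 IU/kg is 5 × 12.5 = 62.5 IU (0.625 mL, 12.5% of a 500 IU vial) at 12.5 kg, and 5 × 45 = 225 IU (2.25 mL, 45%) at 45 kg. If an additional vial is opened for this, its entire content is not used.

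**When no additional vial is needed.** A 20 kg child on 20 IU/kg receives 400 IU. Moving to 500 IU gives 25 IU/kg, exactly +5, from the vial already in use. At 10 kg, 20–40 IU/kg is 200–400 IU, and adding 5 IU/kg gives 250–450 IU, still within one vial.

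**Weekly consumption.** Injections per week run from 7/3 to 7/2.

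- Planned regimen: 20 × 7/3 = 46.7 to 40 × 7/2 = 140 IU/kg/week, a threefold range.
- A 5 IU/kg step adds 11.7 to 17.5 IU/kg/week.
- One whole vial at 20 kg adds 25 × 7/3 = 58.3 to 25 × 7/2 = 87.5 IU/kg/week.
- One such child among 5 raises the age-group mean by at most 58.3/5 = 11.7 to 87.5/5 = 17.5 IU/kg/week, against 2.3 to 3.5 for a 5 IU/kg step. These are upper limits, because they treat the increase as applying throughout.

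**The case against.** The rule is worded with latitude: it is a recommendation, the step is approximate, and it is said to depend on vial content. Section 5.4.2 does not require whole-vial dosing at the start, and the reasoning in 1.4.1 concerns the PK dose. A reader might infer that the rule cannot be followed in children at all. The 20 kg example above, 400 to 500 IU, shows otherwise. That objection stands, and it confines the contradiction to cases where an additional vial is needed.

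Other stronger readings also fail:

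- **A tenfold step.** At 10 kg one vial is 50 IU/kg, but adding it to a whole vial means starting at 50 IU/kg, above the section's range. From within the range, a 5 IU/kg increase at that weight needs no second vial.
- **Exceeding 40 IU/kg as a breach.** The rule itself takes a child on 40 IU/kg to about 45, and the investigator may choose other regimens. What is missing is a statement of how escalation relates to the range.
- **Overdose reporting.** Section 7.3.7 speaks of administration "at a dose higher than specified in the protocol", but it also requires that the dose exceed the known therapeutic dose to a clinically relevant degree. A result of 50 IU/kg is within doses set elsewhere (5.4.1, 5.4.3, 5.4.4). Results at lower weights, such as 66.7 IU/kg at 15 kg, are higher, but the documents do not say what the known therapeutic dose is. No effect on reporting is shown.
- **Uninterpretable endpoints.** TABR, SABR and consumption are descriptive and already pool the threefold planned range plus discretionary regimens. Doses and dates are recorded, and consumption per child would show a larger dose.

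The latitude in the wording does not remove the conflict. When an additional vial is opened, its whole content and a step of about 5 IU/kg do not agree at any weight in the table.

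**Conclusion.** The point holds for escalations that need an additional vial. A whole additional vial gives a step of about 11 to 40 IU/kg in children of an assumed 45 to 12.5 kg who start on whole vials within the planned range, about 2 to 8 times the figure in the text. The mismatch itself depends little on the weight assumption, since agreement needs 100 kg. The step can also take a child above the range in the same section, for example from 25 to 50 IU/kg at 20 kg.

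The reach is limited. Only children who meet the trigger are affected, and the documents give no basis for estimating how many. The primary endpoint rests on baseline PK (3.1.1), collected before prophylaxis starts, and is untouched. Severity is moderate: a dosing figure that disagrees with its own condition, at low cost to put right.

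One limit on the reading: this protocol is version 02, for Ukraine only. SAP 1.2 also cites version 03, which is not among the documents, so whether the sentence remains there is unknown.

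**What to change.** The sponsor should reconcile section 5.4.2 and the Study Outline with the vial sizes in 5.1 and the whole-vial reasoning in 1.4.1, so that the stated step and the vial condition agree across the trial's weight range. The text should also say how an escalated dose relates to 20–40 IU/kg. Which step or vial condition applies is for the sponsor's clinicians; none is proposed here.

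In the SAP, flag each child whose prophylactic dose was raised and list the date and the step actually given in IU/kg. Section 7.2.2 already collects doses and dates, so this needs one listing and no extra visits or patients.

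TABR, SABR and consumption before and after escalation may be shown as an optional descriptive display. It should carry two caveats. The periods may be short. And because escalation follows frequent or serious bleeding, a lower rate afterwards is partly regression to the mean and should not be read as an effect of the higher dose.
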